not otherwise specified) across collaborative clinics in the US and Canada; and (2) examine predictors of treatment response in up to 80 youth (up to 20/site) with bipolar spectrum disorders (BD I, II or OSBD) followed over 12 months, using harmonized treatment methods and instrumentation. We will measure mood instability (rapid fluctuations in moods, even when youth are not in an illness episode) and an inflammatory marker based on a blood test (C-reactive protein) as predictors of outcome. Accomplishing these objectives will set up the infrastructure for open trials of novel treatments for youth at high-risk for BD spectrum disorders.

Year 1 has several milestones by which progress can be measured: protocol development, IRB approval, cross-site harmonization of assessment and treatment methods, validation of a mood instability phenotype, and development of an open trial infrastructure for novel treatments. Developing standardized procedures across study centers (and eventually, nations) is a critical component of developing treatment algorithms for use in a wide variety of health settings, with culturally heterogeneous populations of youth with or at risk for BSDs.

(3) Background and Significance

Cross-site networks have led to huge advances in the treatment of childhood diseases. Notably, the development of a pediatric cancer network has led to significant reductions in childhood mortality: doctors are now able to focus on dose optimization for individual patients rather than searching for new drugs to treat heterogeneous populations. Similar advances could come from a multi-center network devoted to understanding and treating pediatric bipolar illness. The timing for developing a collaborative bipolar network (CBN) is right because of advances in the reliable diagnosis of *syndromal BD* (types I or II) in children and adolescents and the identification and early treatment of youth at *high risk for BD*. Much of this work has been done at the member sites. Notably, investigators at University of Pittsburgh Medical Center (UPMC), VCU, UCLA, Colorado and collaborators have developed operational criteria for other specified bipolar disorder (OSBD), which presents in youth as brief and recurrent subthreshold periods of mania or hypomania. OSBD is a neglected bipolar subtype that is genetically and clinically very similar to BD I and II, but can be associated with psychosocial impairment that exceeds BD I and II

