Adolescent Longitudinal Interval Follow-up Evaluation (A-LIFE). To examine the severity of youths’ mood symptoms at each study interval, independent evaluators will administer the A-LIFE interview to the youth and one parent, and rate each week of the prior 6 month interval (i.e., 6 months prior to intake, then months 1-6 and 7-12) on Psychiatric Status Ratings (PSRs) of depression, hypomania, mania, and suicidality (Keller et al., 1987). The depression PSR is scored on a 1 (symptoms absent) to 6 (severe symptoms) scale, whereas the mania and hypomania PSRs

will be combined into a single 8-point hypo/mania scale ranging from 1 (no symptoms) to 6 (syndromal hypomania), with scores of 7-8 indicating severe or extremely severe mania. To enhance recall, interviewers query participants as to life events or seasonal change points (e.g., beginning of school year, holidays) during the retrospective interval that might have been associated with changes in mood. Interrater reliabilities (intraclass rs) for weekly PSRs for depression and hypo/mania in a past multisite study were 0.88-0.99, calculated across raters at three sites ([name], [name], et al., 2020).

The ALIFE will enable us to capture the timing of symptom recovery (depression and hypo/mania PSRs ≤ 2 for ≥ 8 consecutive weeks) and recurrence or first episode onset (PSRs ≥ 5 for ≥ 1 week for hypo/mania or ≥ 2 weeks for depression). We will collect data on the participant's variability in episode length to determine whether the criteria for OSBD capture the unique cycling patterns of youth who are at high risk for BD I or II.

5.i.2. Questionnaires

The following questionnaires will be administered to the youth and at least one parent at baseline, 6 months, and 12 months.

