Childhood Trust Events Survey – Children and Adolescents (child re: self)	History of traumatic events	X			
FAMILY FUNCTIONING					
Perceived Criticism Scale (4 items)	Low/high expressed emotion	X	X	X	X
Conflict Behavior Questionnaire	Family conflict	X	X	x	x

CHILD FUNCTIONING					
A-Life (weekly Psychiatric Status Rating grid)	Depression and mania syndromal status	X	X	X	X
Ecological Momentary Assessment of Mood States (Chorus Platform)	8 mood items, queries every 2 hours for 7 days	X		X	X
Moods and Feelings Questionnaire	Depression/irritability	X	X	X	X
Parents' Online Weekly Evaluation and Rating Scale (POWERS) on Chorus Platform	Symptom severity weekly		X		X
Children's Affective Lability Score	Mood Instability	X	X	X	X
CGAS/CGI Severity	Functioning Scores	X	X	X	X
Drug Use Screening Inventory	Usage score	X		X	
SCARED Anxiety Q'nnaire	Anxiety score	X		X	
KINDL Quality of Life	Quality of life	X		X	
Treatment Utilization Form	Personal psychiatric service use		X		X
Physician's Report Form	Filled out by MD after every med visit				

5.j. Mood Instability

Mood instability is a behavioral phenotype that characterizes many disorders, but appears to have strong prognostic utility in early-onset BD. Mood instability refers to frequent, sudden, and unpredictable shifts in emotional states. We will use multi-method assessments to capture mood instability during various phases of the study.

1. The Children's Affective Lability Scale (CALS Gerson et al., 1996) is given in both child-rated and parent-rated versions. It consists of 20 items covering the prior 3 months: "Suddenly becomes tense or anxious...has bursts of being overly affectionate or silly....starts to laugh or cry...suddenly appears sad, depressed, for no reason." It is a measure of mood lability, and has subscores for elevation/activation, irritability, and anxiety-depression. It will be given to parents and children at each study interval.
2. Ecological momentary assessments. On six consecutive days (4 week days, 2 weekend days of the first week following the initial assessment), we will issue six prompts on the

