Treatment Utilization Form ([name] et al., 2020). This brief form asks parents to summarize the child's use of health services in the last 3-6 months, including medications, psychotherapy, or other treatments. Parents also make a rating of the child's compliance or consistency with medication regimens.

6. Treatment Protocols

6.a. Pharmacotherapy for Primary Mood and Comorbid Disorders

The youth who enter this study will have had clinically significant elevations of depressive, manic, or hypomanic, or comorbid symptoms that will usually warrant psychopharmacological intervention. Psychiatrists associated with the study will undertake pharmacological interventions using good practice guidelines for high-risk youth ([name] et al., 2017) and children or adolescents with established BD I or II (Yatham et al., 2018). If the child is not taking mood stabilizing or atypical antipsychotic medications, these agents may be started; if the child is already taking medications, they may be augmented with other agents or dosages increased. In some cases, an existing agent will be discontinued (e.g., a child is clearly rapid cycling following initiating an SSRI). We will not put the child at further risk by delaying medication treatment.

We will not require that the child take medicines to be in the study. They may be followed over time without taking medications, as long as we are able to collect information on medications and medication adjustments from their community psychiatrist. Youth and parents who opt to see their own doctors will be asked to sign HIPAA Research Authorization forms to allow this communication.

As indicated, there will be a **Pharmacotherapy Advisory Committee** available to the treating psychiatrist for consultations about treatment of complex cases. However, psychiatrists will not be under any obligation to follow a specific protocol; they will be encouraged to treat each child as per best community practice, as outlined in the above-cited guidelines.

If willing, all participants will be assigned to a psychiatrist upon entry into the study, with the understanding that the cost of care will be borne by the child/family's own insurance or other payment options the child's family has arranged. Psychiatric treatment is a regular part of the community care of bipolar disorder and would be necessary whether or not the child took part in

the study. These terms will be spelled out in the consent and assent forms.

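### Mood instability is scored at fixed visits whatever the mood state and first modelled without covariates, so an unadjusted CALS association with later PSRs can partly reflect concurrent severity

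*Protocol*

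**What the plan says.** Protocol, section (2) Specific Aims, describes mood instability as "rapid fluctuations in moods, even when youth are not in an illness episode" and lists it with C-reactive protein as a predictor of outcome. The Year 1 milestones include "validation of a mood instability phenotype".

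Section 5.j gives the measurement plan: "We will use multi-method assessments to capture mood instability during various phases of the study". For the CALS, "It consists of 20 items covering the prior 3 months"; the scale "has subscores for elevation/activation, irritability, and anxiety-depression", and parents and children complete it at every study interval. EMA runs at entry and in the week after the 6- and 12-month interviews, and lability is derived by modelling change across prompts. Neither measure depends on mood state.

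On entrants, section 6.a says: "The youth who enter this study will have had clinically significant elevations of depressive, manic, or hypomanic, or comorbid symptoms".

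Section 5.i.1 has evaluators use the A-LIFE to "rate each week of the prior 6 month interval", covering the 6 months before intake, months 1-6 and months 7-12. Recovery requires PSRs of 2 or less for at least 8 consecutive weeks. Episode level is a PSR of 5 or more.

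Section 7 makes PSR severity the primary outcome and fits the models first with no covariates. As possible covariates, in an example about sites, it names sex, diagnosis, race, ethnicity and socioeconomic status. It gives no model for mood instability.

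**The concern.** The CALS subscores lie close to the symptom domains that the PSRs rate, and a 3-month look-back can take in symptomatic weeks. Recent severity is also a natural predictor of later severity. If severity in the CALS window raises both the CALS score and later PSRs, an unadjusted model will show CALS predicting outcome even when lability adds nothing.

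At stake is how a milestone is read. The network could report a validated, prognostic instability phenotype when the data show only that youth who were more ill stay more ill. A phenotype of interest because it also exists outside episodes needs at least one analysis that looks there, and neither 5.j nor section 7 provides one.

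**Working it through.** **The plan's own figure.** The only sample-size arithmetic is in section 5.c: 20 completers per site at 80% completion needs 20/0.80 = 25 recruits per site, which reproduces. Four sites give 80 completers, the n used below. The protocol states no alpha, power or effect size and no correlation between instability and severity. Those used here are assumptions.

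**Windows.** Three months is about 13 weeks. Recovery needs 8 weeks, so a youth who has just met it can still have about 13 - 8 = 5 symptomatic weeks inside the CALS window. This shows that overlap is possible, not how common it is.

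**PSR coverage.**

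| Score | Same-window PSRs available? |
|---|---|
| CALS at baseline, 6 and 12 months | Yes, from the A-LIFE at the same visit |
| EMA at baseline | Yes, first week of months 1-6 |
| EMA at 6 months | Yes, first week of months 7-12 |
| EMA at 12 months | No, it follows the last A-LIFE |

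**False declarations.** Let S be severity in the CALS window, correlated a with CALS and a with later PSR, with no direct link from CALS to later PSR.

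- Induced correlation: r = a × a.
- Chance of significance (two-sided 0.05, n = 80, Fisher z): Φ(z√77 - 1.96) + Φ(-z√77 - 1.96), where z = atanh(r).
- For a = 0.5: r = 0.25, z = 0.255, z√77 = 2.24, probability 0.61.
- After adjustment for a PSR with reliability ρ, the remaining partial correlation is a²(1 - ρ)/(1 - ρa²), tested with √76.
- For a = 0.6 and ρ = 0.88: 0.36 × 0.12/(1 - 0.317) = 0.063, probability 0.09.

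| a | Induced r | Unadjusted | Adjusted, ρ = 1 | ρ = 0.88 | ρ = 0.7 |
|---|---|---|---|---|---|
| 0.3 | 0.09 | 12% | 5% | 5% | 6% |
| 0.4 | 0.16 | 29% | 5% | 5% | 8% |
| 0.5 | 0.25 | 61% | 5% | 6% | 13% |
| 0.6 | 0.36 | 91% | 5% | 9% | 25% |

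Simulation (20,000 runs per row) agrees to within about a percentage point. The 0.88 is the lowest interrater value that section 5.i.1 quotes from a past multisite study; 0.7 is assumed.

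**Predictor-by-time form.** Section 7's site example tests a between-subject factor by time, with baseline as the first repeated PSR. Put CALS in that role and take S as the baseline PSR. The correlation of CALS with change is then (a² - a)/√(2 - 2a), which runs from -0.18 at a = 0.3 to -0.27 at a = 0.6. In simulation this is significant and negative in 35% to 68% of runs. The artefact changes sign but does not go away.

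**The case against.** **This belongs in a SAP.** The remedy is a covariate and a subset analysis, section 7 rules neither out, and the PSRs are already collected. That stands in part: a SAP that is not shown may already do this. But the protocol itself sets the instruments, their windows and a covariate-free first fit, and followed as written these can credit instability with the effect of severity.

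**Scoring in every mood state fits the aim.** A reader might infer that fixed-visit scoring contradicts Aim 2. It does not. The aim's wording means also outside episodes, not only there, and 5.j's own definition carries no episode condition.

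**The overlap may be small.** A reader might infer that the phenotype largely re-measures episode severity. No figure in the protocol supports that. Sharing more than half the variance needs a correlation above 0.71, and the values used here share 9% to 36%. The sample CALS items describe abrupt, unexplained shifts rather than sustained mood. EMA lability is scored from change, so the argument is weaker there, and the calculation covers only CALS. Section 6.a speaks of past elevations, including comorbid symptoms, and does not place an episode in the 3 months before intake; entry requires a diagnosis, not a current episode. All of this stands.

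**The calculation assumes its answer.** Instability's own effect is set to zero and the correlations are chosen. True: it shows what could happen over a plausible range, not what will. The 5% after adjustment also needs error-free PSRs, and weekly ratings recalled over 6 months are not error-free.

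**Conclusion.** The point holds in a limited form and should be addressed. As the protocol is written, an unadjusted CALS association with PSR outcomes cannot be separated from the effect of concurrent mood severity, so on its own it would not validate the phenotype or show that it is prognostic. The same applies to EMA, less strongly.

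The size is unknown. With correlations of 0.3 to 0.6 on both paths, n = 80 and a two-sided 5% test, all but the n assumed, a null instability effect is declared in about 12% to 91% of studies. PSR adjustment brings this to about 5% to 9% at reliability of 0.88 or better, but leaves up to about 25% at 0.7. The documents do not support saying that the measures conflict with the aim, or that instability scores are mostly severity.

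**What to change.** Add to sections 5.j and 7:

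1. Report the unadjusted association as planned, but base any claim that instability is prognostic or validated on an analysis that adds the mean depression PSR and mean hypo/mania PSR over the same 3 months as the CALS score.
2. For EMA, add the PSRs of the same week at baseline and 6 months. State that no A-LIFE covers the 12-month EMA week.
3. Use PSRs after the window as the outcome, so that the window's PSR is not both outcome and covariate. The 12-month CALS has no later PSR and can support only concurrent analyses.
4. As a sensitivity analysis, repeat this in windows with no week at the protocol's episode level.

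The cost is a few lines of text and some programming, with no new visits or data. The adjusted estimate will be smaller and less precise. If lability itself raises PSRs, adjustment removes some real signal, which is a reason to show both results. PSR error leaves residual confounding. The episode-free subset will be smaller, and subthreshold severity still varies within it.

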8. POTENTIAL RISKS

This study will be of minimal risk to participants. There is a low risk of harm to youth with BD spectrum disorders from receiving the good practice pharmacotherapy procedures or assessment instruments outlined in this protocol. Pharmacotherapy is not required and when parents and children opt for it, the study psychiatrists will follow standards of best practice, as outlined earlier. Parents can enroll their child in pharmacological treatment from a physician of their choosing if they do not want to see one of the study-affiliated psychiatrists. In these cases, the study psychiatrist will conduct an initial diagnostic evaluation and recommend a treatment plan to the youth's outside psychiatrist, unless the family does not want this recommendation. Assessment reports generally consist of an evaluation summary followed by phone calls if the

outside physician would like further clarification. The youth and parents must sign our HIPAA release form for us to send this treatment information. Of course, the outside physician and family are under no obligation to follow the recommendations of the study psychiatrist.

Children and parents may at times feel inconvenienced by the time required to complete the research assessments. The assessment battery has been designed to minimize participant burden but to cover the domains and constructs relevant to the study's hypotheses (see table above). Participants will be compensated for completing each assessment battery (\$40 for initial intake assessment, \$20 for the 6- and 12-month assessments). Research interviews will be scheduled at the times (for example, after school; immediately following the medication visits) and locations most convenient for the youth and family, or (if participants prefer, or COVID safety regulations demand it) via a Zoom telehealth visit. Participants who leave the study early will still be paid for those research assessments completed up to that point. The default arrangement will be that compensation will be divided evenly between parents and children, although there may be cases where the family would prefer another arrangement.

Participants may at times experience sadness or discomfort when discussing family issues, personal problems, or psychiatric symptoms, but no more than they would if they took part in psychotherapy or pharmacotherapy sessions in the community. Discussing the child's psychiatric problems may at times be upsetting to the child or family. If these reactions occur, the research staff, all of whom are trained psychiatrists and psychologists will offer the participants emotional support and validation. Clinicians will acquaint the child and family with methods to manage and control mood symptoms and enhance day-to-day functioning. Participants will also be informed that they can receive and follow-up on referrals for counseling outside of the study at any time, without being dropped from the protocol.

The children and adolescents recruited for this study are believed to have already developed or are at high risk for developing BD. Children with BD are vulnerable to disturbances in school and social functioning, substance abuse, and suicidal ideation or actions. There is no reason to suspect that rates of these illness complications will be higher if the adolescent receives treatment in the study instead of a community treatment setting. Because of the careful pharmacotherapy and follow-up protocols administered in this study, rates of adverse events associated with the disorder may be lower than if patients were treated in the community.

Participating in alternative treatments in the community has its own risks. Treatment in the community often does not explore the illness management strategies relevant to bipolar spectrum disorders. Pharmacotherapy as practiced in the community will usually involve the same classes of medications as proposed here, but may not include the careful pharmacological oversight by experts provided in this study.

9. ADEQUACY OF PROTECTION AGAINST RISKS

9.a. Recruitment

Training of staff. All study research staff will be trained in recruitment and informed consent procedures before collecting data for this study. We will develop a study procedures manual that clarifies how to explain the study to participants and parents and address questions about medications, assessments, privacy, or other study-related matters. Training will require that study staff read through and discuss the manual and participate in role-plays of the recruitment and informed consent process (for example, how to determine if the child and parents fully understand the protocol before signing informed consent or assent documents). The PIs at all sites will carefully supervise the recruitment of all study participants. All research staff proposed for the study have received on-line CITI human subjects training.

Referral to the program. Recruitment will start when a case is referred to the project by a treating psychiatrist or therapist, or by the family itself. When patients are referred by a mental health professional, this professional will give the participants a copy of a study flyer explaining the purposes and basic design of the study (attached). If the parents express interest, there are two options for contacting the study personnel: (1) the treating clinician will ask the child and one of his or her parents to sign a HIPAA Authorization Form. The purpose of the form is to obtain permission from the prospective participants for the treating clinician to release protected health information (name, age, working diagnosis, address, telephone number) to the research team. This will enable the team to contact the participants to determine their eligibility. A copy of the signed authorization form will be provided to the participants and placed in the medical chart; (2) if the prospective participants are not comfortable signing the form, or would like more time to think about contacting the research personnel, the psychiatrist or therapist will give them the study flyer so that they may contact the study investigators themselves.

Telephone Screening Interview. After referral to the program, the project coordinator at each site will initiate the Script to Phone Screen Potential Participants, conducted with one or both parents (see attached). The coordinator will begin by explaining that the study offers a diagnostic evaluation, pharmacotherapy, and follow-up research assessments. Families will be told that their child will receive a full diagnostic workup (including evaluations from a psychologist and a psychiatrist) and, if appropriate, pharmacotherapy as administered by a study psychiatrist for one year.

The Script to Phone Screen Potential Participants (attached) asks the parent to clarify the child's reasons for referral to the program, depression, mania, or hypomania symptoms over the past 6 months, and current medication and psychosocial treatments (if any). No diagnoses will be made at this point. Instead, if the child appears to meet the study's inclusion criteria, an appointment will be set for a first meeting. Informed consent and assent forms will be mailed to the participants so they can review these forms and assemble their questions prior to the first meeting.

9.b. Consent Procedures

Initial meeting, study description, and KSADS Interviews. During the initial meeting, to be held at the site's clinic (for UCLA, CHAMP Clinic A8-256 UCLA-NPH and associated interview rooms), the project coordinator will explain the study procedures and treatments to the child and their parents. The coordinator will address the family's concerns about the study together in a conjoint meeting and separately (i.e., child alone, parents/siblings alone) in break-out portions of the same session. The coordinator will explain the IRB-approved consent and assent forms (youth assent form, parent permission forms) and assure that the participants have had ample time to read and review them before signing. The parents and children will once again be informed, via information given orally and in the consent and assent forms that the study involves research assessments, and that their participation is optional. Access to pharmacological intervention is optional.

The research staff will determine each individual participant's level of comprehension of the material presented, based on whether the subjects are able to paraphrase the information in the consent or assent form, to comprehend it adequately, and to ask reasonable questions about

their participation. The coordinator will ask the participants to explain back to her (in their own words) how they understand the procedures and what will be required of them, any risks or discomforts involved, the possible benefits of the study, the voluntary nature of the study and their right to withdraw at any time. Subjects who wish to do so will be encouraged to speak separately with other family members, friends, and physicians about the consent or assent forms before making their decision to participate.

If the family has any prior treatment relationship with the project coordinator, the PI, or any of the other study clinicians, the consenting procedure will be carried out by a staff member who is not the current therapist. This will avoid a situation in which family members feel obligated to participate.

The parents will be told that their own emotional/behavioral functioning will be evaluated, in addition to the child's. **All participants will understand that their acceptance or refusal will in no way affect their (or the child's) ability to receive appropriate psychiatric care from their chosen providers, and they are free to withdraw their consent and discontinue participation in the study at any time without any penalty.** If the family needs more time to think about the procedures and consent forms before signing, a second session will be scheduled. All remaining questions that were not addressed in the first session will be answered by the project coordinator at this second session or, if the family prefers, by the PI.

In cases of youth who meet OSBD (high risk) criteria, we cannot be certain whether they will develop a full episode of mania or depression during the study interval. To avoid the negative effects of diagnostic labeling, we will explain to children that they are participating in a study of mood swings, and specifically, what kinds of treatments are helpful in stabilizing moods and improving functioning at school, with friends, and at home. If parents or siblings ask whether the child will get bipolar disorder, we will explain that having a familial predisposition to the disorder, even with subsyndromal symptoms, does not necessarily mean an inevitable trajectory toward the disorder. If parents or youth desire it, we will give them statistics on the likelihood of developing BD if one has a first-degree or second-degree relative with the disorder, making clear that many protective and risk factors can affect a child's developmental trajectory and his or her likelihood of developing the illness.

Thus, the consenting procedure will consist of four key components: (1) consent or assent will be obtained by research personnel who have completed all required human subjects and

HIPAA training; (2) the subjects will be consented or assented in a quiet setting that is free from distraction; (3) the subject's autonomy and comprehension will be assessed by asking them, after the study is explained, to explain back to the researchers the purposes and procedures of the study in their own words; and (4) all participants will receive a copy of their consent or assent form.

9.c. Protections Against Risk

The PIs and study staff will maximize each participant's (including the parents') safety through providing crisis intervention, recommendations or referrals for adjunctive medical/pharmacological interventions, and when necessary, referral to inpatient, partial hospital, or intensive outpatient treatment. All research personnel have been trained by the PIs to recognize early signs of mood escalation or deterioration. Research staff will be continuously supervised by the PIs and Project Coordinators and instructed to inform the attending psychiatrist and PI if a child is showing signs of mood escalation or deterioration.

9.d. Maximizing Privacy and Confidentiality: Access to Subjects' Identities

During the initial meeting, the project coordinator will explain the study procedures and treatments to the child and their parents. Privacy will be assured during the consenting process. Participants will be given ample time to read the consents/assets and ask questions (see Consenting Procedures).

All of the medical and clinical information obtained during therapy sessions, interviews, or questionnaire assessments will be kept confidential, unless participants provide a written request for release of information. All guidelines of the HIPAA privacy act will be followed. Confidentiality assurances will be provided to participants via initial written consent and oral explanations throughout the study.

The videotapes, audiotapes and questionnaires will be retained for research purposes only. When not in use, the tapes will be kept in locked research laboratories which are only accessible to project research staff. Tapes will be kept for 10 years after the study has been completed and then erased. If participants would like to review any of the tapes they may do so. Tapes will be erased if the participant so desires. To help assure the confidentiality of participants, tapes and questionnaires will only contain numbers and not names. Each individual

will receive a unique 5-digit I.D. number, with the first digit referring to site and the next three digits their order in the randomization. Lastly, parent and child data are identified with codes that indicate the respondent to a particular interview or questionnaire (e.g., 0=child, 1=mother, 2=father). Data will be stored in password-protected computer files in a centralized database on a HIPAA-compliant UCLA server. The site will keep a list of its pairings of names and participant identification numbers. This list will be kept in password-protected computer files in the site PI's or project coordinator's offices, separate from any of the paper and pencil questionnaires or numbered digital audio- or videotapes.

The findings from this study will be published in journal articles or books. However, the participants' names and all other protected health information will never appear in these writings. Data will be analyzed at the group rather than the individual level.

9.e. Limits to Confidentiality

If the researchers have reasonable cause to believe that child abuse or neglect is occurring, or there are circumstances which might result in child abuse or neglect, they will comply with state laws by filing a child abuse report with the state's Department of Child Protective Services. The same procedures apply to instances of domestic violence or elder abuse. In the unlikely event that materials from the study are court-ordered for use in a custody or other court hearing, the project staff members will make every reasonable effort to protect the confidentiality of the participants. They may, however, have to respond to these subpoenas as they would with any client under their care.

If the research staff believe that the adult or child participants are at risk of harming someone else, they are required to take necessary actions. These actions include notifying the parent of the participant's intentions, notifying others who might be affected (i.e., intended victims), or notifying the police or the Department of Child Services. In these cases, the research staff will be unable to preserve the adult's or child's confidentiality. These limits to confidentiality will be spelled out in the participants' consent and assent forms.

We will notify parents if we learn that the child is actively abusing alcohol or drugs in a way that is life-threatening or otherwise a danger to themselves or others. If a teen participant has experimented with a drug or alcohol on a single occasion, notifying the parents may not be indicated. Nonetheless, it will be necessary to monitor this behavior in the psychopharmacology

or family sessions. If we disclose these behaviors to parents, we will offer family intervention sessions to help resolve family conflicts and introduce preventative measures. We will coach parents on how to communicate and problem-solve with the child regarding the self-injurious behavior, and counsel the youth on how to discuss these matters with their parents.

9.f. Chorus Mobile App Platform and Data Protection

The MyCoachConnect online survey assessments will be provided through the Chorus Platform. Chorus was developed by [name] at UCLA, and the internet protocol address is owned by the UC Regents. Chorus is a web platform that allows individuals to create their own automated text-messaging, interactive voice and mobile web applications in an easy-to-use and accessible visual web interface.

Chorus is hosted on a secured, SOC2 Type 2-compliant server infrastructure and is HIPAA-compliant. Chorus has been used in over 50 IRB-approved research studies, including with collection of PHI. All data sent to or from the server and Chorus apps are transmitted over encrypted, industry-standard connections like SSL. The server is protected using standard practices including being located behind a network firewall and accessible only by designated users. No data are stored locally on user's devices (such as local browser storage or temporary storage) that access Chorus apps.

The Chorus platform has been approved by the Office of Information Security at UCLA for collection and storage of PHI in research projects as well as patient care activities. The Chorus website uses standard SSL technology to encrypt all traffic to and from the server over HTTPS connections. Server management is conducted via encrypted SSH connections. There are standard practices for backup and encryption of data. Security, backup, and disaster recovery protocols are overseen and approved by Chorus, Inc.

For each stage of the research process, the following procedures will be implemented:

1. Training staff on data sensitivity and data safeguards being employed.
2. Processing sensitive data in a centralized location with established access control procedures.
3. Electronic files used by study staff will be stored on secured, password protected computers accessible only to study staff members.

4. Storing sensitive hardcopy in locked files when not in use.
5. Restricting access to shared disk files through appropriate use of file permissions.
6. Printing sensitive material only when absolutely necessary. When it is necessary, project staff will ensure that an authorized person is at the printer when the sensitive material appears.
7. Using Certified mail, return receipt requested, for sensitive data and Registered mail for very sensitive data when transferring materials by mail.
8. Re-training staff and reviewing sensitive data inventory and data safeguards annually.
9. Reporting all serious violations of the Data Safeguarding Plan in writing to the Principal Investigator, with a copy to the UCLA Privacy Resource Office.

9.g. Managing Risks Related to Blood Assays

Participants may experience brief physical discomfort associated with the blood draw. Any participant who shows an adverse reaction to a blood draw will be treated on site. At UCLA, the blood draws will occur either at the Cousins Center for Psychoneuroimmunology, which has been conducting these studies for many years; or in a UCLA CHS laboratory room with a trained, licensed phlebotomist. Participants may experience brief anxiety related to the blood draw. They will be accompanied to the blood draw by a study staff member and their parent to help alleviate any anxiety that may arise prior to the blood draw.

9.h. Maximizing the Participants' Safety Through Appropriate Pharmacotherapy

To reduce the risks of negative outcomes, we will implement the carefully supervised medication protocol (above) to assure that, when medications are warranted, psychiatrists proceed in a manner that is consistent with good practices in the empirical literature. The study coordinator will explain that the study psychiatrist who conducts the initial evaluation may recommend medications to help stabilize the participant's mood. They will make clear that the study is committed to using best available practice procedures, that the child will not be experimentally assigned to receive a specific medication, and that if new and relevant information about medication efficacy or side effects is published during the course of the child's treatment, the child's treatment regimen will be amended accordingly. The coordinator will also make clear

that taking medication is not a requirement for participating in the study, and that the costs of medication management will be borne by the participant.

Study psychiatrists experienced in treating childhood mood disorders, all of whom will be supervised by internationally-recognized experts from the study's pharmacotherapy oversight committee (Drs. [name], [name], [name], and others), will apply criteria set forth in the study pharmacotherapy protocol to assure best practice administration of medications.

